One final protection involves the disclosure by study participants ages 14 and under that they have had sex with partners who are at least 24 months older than the minor and 15 to 17 years old that they have had sex with partners who are at least 36 months older than the minor. Mississippi's law requires immediate reporting of these cases to the Mississippi Department of Human Services (MDHS). [name] has created a protocol that will be applied to this circumstance, should it arise. It is important to note that our assessment instruments do not ask study participants about the age of their sex partners. However, we do clearly recognize the possibility that young male study participants may volunteer such information to the study staff during interviews or in the course of the assessments. In brief, clinic policy requires that the person to whom the information was disclosed should immediately report to MDHS Child Protective Services the incident by calling the statewide toll free [contact]). The report is then screened by a MDHS supervisor to decide whether it should be investigated. Thus, if a minor in our study discloses having sex with an adult (at least 36 months older than the minor) this mandatory reporting protocol is activated. Any male study participant ages 17 and under will be told that the health department is obligated to report to the state any instance of sex with older men (if at least 24 months older than the minor for those 14 and under and 36 months older than the minor for youth ages 15-17). [name] employs three full-time case managers who are trained counselors and will be on-hand to handle instances where a 15-17 year old discloses sex with an adult to a member of the research staff. The case managers provide additional evaluation to assure the welfare of the minor.

Adverse Reactions from Parent/caregivers. The project will be described as an intervention developing as building healthy adolescent relationships and acceptance of straight and gay adolescents; it will not disclose the adolescent's private behaviors or attitudes; and will not

require adolescents to disclose any sexual behavior. However, it is possible that some parents/caregivers will discover their son is non-heterosexual during the course of the study. Many of the enrolled nHBAM will have previously disclosed their non-heterosexual identity to parents/caregivers thus we are primarily concerned here with those who have not done so in the Adverse reactions from this discovery may include verbal or physical threats or abuse, or various forms of physical neglect (asking the adolescent to move out) and abuse. Our plan is twofold: 1) avert disclosures that may be dangerous in any way, and 2) mitigate harm when signs of retribution first occur. To avert potentially risky disclosures we will guide nonheterosexual Black adolescent males through the completion of a Self-Safety Evaluation tool that we will create. This tool serves as a "best possible" method of helping non-heterosexual Black adolescent males make the decisions regarding what personal information to discuss with their parents, such as expressing their non-heterosexual identity. The tool helps participants anticipate likely reactions, based on past history, and identify trusted available social supports and safety resources, including project staff. Staff will be available to review the results of the Self-Safety Evaluation with the participant if needed and will follow-up with the participant if any adverse reactions are reported. If research staff learns of any verbal, emotional or physical abuse from a parent, he/she will immediately notify [name] who, in turn, will exercise any of several options: 1) initiate mandatory reporting as required by state law, 2) notify local child protective service authorities regarding the situation, or 3) withdraw the adolescent from the study as a safety precaution.

Potential Benefits of the Proposed Research to the Subjects and Others

Importance of Knowledge to be Gained. All phases of the proposed study will provide important information for the development of HIV prevention interventions for non-heterosexual Black adolescent males. We hope that our intervention will be successful in reducing HIV risk behavior among non-heterosexual Black adolescent males and think that the clear examination of these questions outweighs the previously mentioned risks. The effectiveness of a tailored, scalable, online HIV prevention intervention is severely understudied with this population. Given the significant risk of HIV infection among nHBAM and the lack of easily accessible prevention interventions tailored specifically to nHBAM, the knowledge to be gained from this research is significant. The risks to participants are reasonable in relation to the importance of the knowledge to be gained.

Reimbursement for Time and Effort. Participants (approximately 15 non-heterosexual Black adolescent males, 15 parents/caregivers) will be reimbursed \$30 for focus group participation. Stakeholders will be reimbursed \$50 for focus group participation. Community Advisory Board members (4 non-heterosexual Black adolescent males, 4 parents/caregivers, 4 community members) will be reimbursed approximately \$50 for each meeting (12 CAB members x \$50 x 4 meetings/year in Years 1-3). Participants in the Open Trial (10 nHBAM and their parents/caregivers) will be reimbursed \$35 for the baseline and 2-month post-intervention assessments. Randomized Controlled Trial participants (72 nHBAM) will be reimbursed approximately \$35 for the in-person assessments (baseline, 2-months, 4-months, 6-months and 8-months post-intervention). Only those assigned to the waitlist control condition will be eligible for the 6- and 8- month assessments. Randomized Controlled Trial parents/caregivers will be reimbursed \$35 for each of the online assessments (baseline, 2-months, 4-months, 6-months and 8-months post-intervention). Only those assigned to the waitlist control will be eligible to complete the 6- and 8-month assessments. All online assessments will culminate in a screen that provides study participants with a code for an online purchase from Amazon.com. Currently enrolled participants will be incentivized to recruit up to five new participants and will receive an

additional \$10 for each referral that is enrolled in the study (up to a total of \$50). Exit interview or focus group participants will be reimbursed \$100 for the one-hour interview/focus group.

Inclusion of Children, Women and Minorities

Children. In this family-based intervention approximately half of the participants will be youth ages 13-18 and the remaining will be their adult parents or caregivers. The content to be selected in the intervention will be designed and appropriate for children 13 and older. The Development phase of the study will ensure that all material is tailored to the developmental and cognitive level of adolescents and for their parents. Thus, the proposed program is appropriate for adolescent children.

Women. All of the adolescents in the study will be male. The target population for this project is adolescent non-heterosexual males, who are greatest risk for acquiring HIV in the U.S. The proposed project involves a family-based intervention, which provides the opportunity to include parents/caregivers who may be women. It is anticipated that approximately 80% of the sample of parents/caregivers and stakeholders will be females.

Minorities. The aim of our recruitment strategy is for the resulting program materials to be appropriate for Black non-heterosexual males because of their high risk for acquiring HIV. In terms of race, 100% of the enrolled adolescent participants will be Black/African American. Ethnically, 5% or fewer will self-identify as Hispanic or Latino.

DEPARTMENT OF HEALTH AND HUMAN SERVICES (DHHS) "REQUIRED EDUCATION IN THE PROTECTION OF HUMAN RESEARCH PARTICIPANTS"

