Digital consent, enrollment, and follow-up: In light of the COVID-19 outbreak, several of our recruitment sites (i.e. CBOs, clinics, and schools) have either closed or are limiting nonessential visits. This limitation severely impacts our ability to recruit and enroll potential participants in-person for the RCT phase of this project. We are proposing to offer digital consent and enrollment via HIPAA-compliant platforms (i.e. DocuSign, HIPAA-compliant video conferencing platforms). nHBAM identified as eligible, based on an online REDCap screener, will be asked if they would like to be contacted by study staff. Those that indicate they would like to be contacted will then be asked to provide their name, email address, and phone number. UMMC research assistants will follow up with interested parties by phone or email. Those who wish to participate will receive a DocuSign consent form via email from the UMMC research assistant and will be given the opportunity to participate in a video conference call (via HIPAAcompliant video conferencing platform with the UMMC research assistant to review the consent form. The DocuSign consent form will outline study aims and procedures and contains language regarding the risks/benefits of participating in a research study. The online survey data will be de-identified and kept in a password-protected participant log on a secure server. Participants will be given ample time to consider risks of participation and will have the opportunity to ask questions during the video conference. Participants will also be reminded that study participation is voluntary and that refusing to participate or withdrawing from the study at any time will not result in any negative consequences. For the remaining follow-up appointments (at 2- and 4-months, and additionally at the 6- and 8-month appointments for waitlist control participants) participants will be emailed their online REDCap surveys and will receive online gift cards for each completed survey. At the 4-month appointment, nHBAM will be offered a home HIV testing kit, that will be mailed to them by UMMC, in lieu of an in-person HIV test.

Parent or caregiver enrollment: The RCT allows nHBAM into the program before parent/caregiver involvement is requested (with a waiver of parental consent for those under 18) and then prepares nHBAM to safely involve their parent, if possible. More detailed information on the process is shown in the schematic below. nHBAM aged 18 or older

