will be able to provide their own consent, although we will ask for permission to enroll parents/caregivers, if possible and safe for the youth. The project will be described as a general sexual health intervention for adolescent males; it will not disclose the adolescent's private behaviors or attitudes and will not require adolescents to disclose any personal information.

Parent/Caregiver involvement may begin at study entry, at the middle of the intervention or immediately after the 8-week intervention, after the nHBAM has had more time to consider it. Parents/caregivers will be assigned to the same condition as their adolescents.

RCT Phase

- a.) These adolescents are likely to have highly supportive parents who enroll as well. nHBAM will give consent for their study enrollment and permission for the study to contact parents for their participation.
- b.) These adolescents may nominate up to 4 caregivers the project director may then obtain parental consent and parent engagement (less likely than "a') or parental consent and parental agreement for caregiver to enroll in place of the parent. nhBAM aged 18 or older will be able to give consent for caregivers to enroll but caregiver enrollment is not required.
- c.) We will not pressure these adolescents to allow us to make this contact their reticence is a clear sign that a waiver of parental consent is warranted for safety reasons.
- d.) As a result of intervention efforts nHBAM from "c" are asked again at mid-intervention and at the end of the intervention for permission to contact a parent those agreeing may then have that parent become engaged in the study.
- e.) As a result of intervention efforts nHBAM from "c" are asked again at mid-intervention and at the end of the intervention for permission to contact a parent some may agree only for the purpose of gaining parental permission to involve one of four nominated caregivers in the study. nHBAM aged 18 or older will be able to give consent for caregivers to enroll but caregiver enrollment is not required.
- f.) These adolescents will continue under a waiver of parental consent if under 18 and do so without a parent or caregiver being engaged. Adolescents aged 18 or older continue under their own consent.

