Randomization: Immediately after completing baseline assessment, small block randomization (via REDCap) will create groups balanced on age and on the proportion who identify as nHBAM. We estimate that 90% of those enrolled will be nHBAM. 72 participants will provide sufficient power for the analyses (see Data Analysis). Recruitment will continue until 72 nHBAM are enrolled.

Format: Immediately after randomization, participants (adolescents and parents/caregivers) in the active (MySTYLE) condition will receive two secure, HIPAA compliant texts or emails to their mobile phones or preferred indicated device each week for eight weeks and each text/email will contain a link to new media content (overall, at least 120 minutes of multimedia time is planned, not including participant replays, which is comparable to our interactive DVD and to an online RCT conducted by Mustanski and colleagues). (9) The weekly content, as well other content and interactive materials, will be available on their condition's secure website. All nHBAM and enrolled parents/caregivers will each have their own links with separate, but parallel, content (see Figure below in Intervention Conditions). Those participants assigned to the waitlist will be eligible to participate in MySTYLE after they have completed their 2- and 4-month assessments. They then will receive two secure, HIPAA compliant texts or emails to their mobile phones or preferred indicated device each week for eight weeks and complete further assessments at 6 and 8 months. If those enrolled in the waitlist choose to participate in MySTYLE, they will have the opportunity to include their parent mid-intervention. During the 4 months that the participant is on the waitlist, study staff will not engage with the parent.

Intervention fidelity and usage: The twice-weekly video/graphic content will be embedded in the participant's unique REDCap link, providing data on the number of videos viewed by each participant. The participant will not proceed to the next web page (containing options for their weekly practice, etc.) until the video has fully played, but it may be paused and resumed later. The videos/graphics will be posted on the website for repeat viewing. Analytics will be collected on the number of minutes enrolled nHBAM spend viewing project materials, the content accessed, and the number of times any one video was re-played.

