Formative phase and pilot trial parent or caregiver enrollment: Parents will be contacted by phone and written informed consent for a son's participation obtained in person. If the parent (legal guardian) agrees to their son's participation in the project but does not want to participate, the parent and adolescent can nominate "someone important in the life of the adolescent such as other family, teacher, religious leader, or social worker" who will be contacted for enrollment. Caregivers will not be enrolled in lieu of a parent unless the parent agrees. This option of involving a caregiver, rather than a parent, worked well in Project STYLE, and involving a non-parental adult was recently recommended as an intervention option for non-heterosexual adolescents.⁽⁶⁹⁾ Even if a parent/caregiver never participates in the intervention, MySTYLE, may improve the family climate by focusing on healthy family communication, similar to other studies finding an impact without all family members attending sessions.⁽⁷⁰⁾

RCT enrollment: For the RCT phase a waiver of parental consent will be utilized for those under 18 and youth aged 18 or older will be able to provide their own consent. A waiver of parental consent for those under 18 produces a sample that is more diverse in terms of the extent to which nHBAM have disclosed their sexual attitudes to others, their degree of perceived stigma and discrimination, and their perceived support from, and engagement with, parents.

The RCT allows nHBAM into the program before parent/caregiver involvement with a waiver of parental consent for those under 18 and then prepares nHBAM to safely involve their parent, if possible. nHBAM aged 18 or older will be able to provide their own consent, although we will ask for permission to enroll parents/caregivers, if possible and safe for the youth. The project will be described as a general sexual health intervention for adolescent males; it will not disclose the adolescent's private behaviors or attitudes and will not require adolescents to disclose any personal information. Parent/Caregiver involvement may begin at study entry or at mid-intervention, after the nHBAM has had more time to consider it. After the adolescent provides permission to contact their parent/caregiver for enrollment, we will follow the parent/caregiver consent procedures described above in the formative and pilot trial phases. Parents/caregivers will be assigned to the same condition as their adolescents.

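### Before month 4 only the MySTYLE arm can add parents, so comparing all enrolled parents' own reports at 2 and 4 months is not a comparison of randomised groups

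*Combined protocol and SAP*

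**What the plan says.** **Allocation.** The Randomization paragraph states: "Immediately after completing baseline assessment, small block randomization (via REDCap) will create groups balanced on age". It does not say whether a parent's baseline must be complete first. Parents are not randomised separately: "Parents/caregivers will be assigned to the same condition as their adolescents".

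**Parent entry.** "The RCT allows nHBAM into the program before parent/caregiver involvement is requested". After that, "Parent/Caregiver involvement may begin at study entry, at the middle of the intervention or immediately after the 8-week intervention". The RCT enrollment paragraph in the Human Subjects section lists only study entry and mid-intervention, and adds that "we will follow the parent/caregiver consent procedures described above in the formative and pilot trial phases". Youths who first decline "are asked again at mid-intervention and at the end of the intervention for permission to contact a parent"; items d and e present any later agreement as a product of the intervention.

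**Waitlist.** The Format paragraph starts the waitlist's intervention after the 2- and 4-month assessments. It adds: "If those enrolled in the waitlist choose to participate in MySTYLE, they will have the opportunity to include their parent mid-intervention". It also says: "During the 4 months that the participant is on the waitlist, study staff will not engage with the parent". The Reimbursement section nevertheless pays RCT parents for online assessments at baseline, 2 and 4 months, and restricts only the 6- and 8-month ones to the waitlist.

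**Use of the data.** Aim 3 covers parental attitudes and behavior. Parents complete their own versions of the family and relationship scales. The Data Analysis Plan hypothesises better family practices in MySTYLE at 2 and 4 months, tests group differences in linear change, and uses inverse probability of treatment weighting for baseline imbalance. It defines no parent analysis set and no baseline for a parent who joins late.

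**The concern.** Whether a parent appears in the 2- and 4-month data is partly a result of the youth's allocation. The families added late are also unlikely to resemble the others. Item a expects entry families to have strongly supportive parents, while item c treats a youth's reluctance as a sign that the consent waiver is needed for his safety. MySTYLE would therefore be represented by entry families plus converted decliners, and the waitlist by entry families at most.

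The planned methods do not repair this. Weighting on baseline characteristics cannot use a late parent's first score as a baseline, because it follows allocation and may follow exposure. The mixed model cannot recover the waitlist counterparts of late MySTYLE parents, because they contribute no parent scores before month 4. The trial exists to supply effect sizes for a larger study, and the Power paragraph names parenting practices among the major outcomes, so a distorted parent estimate would carry forward.

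**Working it through.** **1. The plan's yardstick.** The Power paragraph gives a detectable effect of .41 SD (alpha 0.05, power 0.80, 72 enrolled, 85% retained, three assessments). A plain two-sample calculation with 72 × 0.85 = 61.2 gives (1.960 + 0.842) × √(4/61.2) = .72 SD. Reaching .41 needs a within-person correlation of about .67 to .84, depending on the model and on whether N is 61 or 72. None is stated, so the figure is neither confirmed nor refuted. It serves here only as a scale. Its N counts youths, not parents.

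**2. When a parent can be added.**

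| Time | MySTYLE | Waitlist |
|---|---|---|
| Study entry | yes | yes, unless the no-engagement sentence is literal |
| Mid-intervention (about week 4) | decliners re-asked | no |
| End of intervention (week 8) | decliners re-asked | no |
| After month 4 | – | midway through the delayed course |

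**3. Composition of the arms.** Assumptions: 36 per arm (the ratio is not stated); 48% bring a parent at entry (the willingness figure the plan cites from a study of under-18s); 25-50% of the remaining MySTYLE youths converted; waitlist entry parents are assessed.
- Entry parents per arm: 0.48 × 36 = 17.3. Decliners: 18.7.
- Late MySTYLE parents: 0.25 × 18.7 = 4.7, to 0.50 × 18.7 = 9.4.
- MySTYLE total 22.0 to 26.6, against 17.3 on the waitlist.
- Late share in MySTYLE: 4.7/22.0 = 21%, to 9.4/26.6 = 35%. On the waitlist: 0%.

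**4. Shift in the arm mean with no treatment effect** = late share × gap between late and entry families.
- Gap 0.5 SD: 0.213 × 0.5 = 0.11, to 0.351 × 0.5 = 0.18 SD.
- Gap 0.25 to 1 SD: 0.213 × 0.25 = 0.05, to 0.351 × 1 = 0.35 SD.
- Gap 0.5 SD with entry enrolment varied: 0.077 × 0.5 = 0.04 SD (75% at entry, 25% converted), to 0.600 × 0.5 = 0.30 SD (25% at entry, 50% converted).

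**5. Shift in the planned contrast.** The plan tests change, so the mean shift is not the bias of that test. Take a random-intercept model with arm, time and arm × time, total variance 1, within-parent correlation .5 to .8 (assumed), late parents 0.5 SD lower with a flat course, and no treatment effect. The expected coefficients are (ΣX′V⁻¹X)⁻¹ΣX′V⁻¹μ. Multiplying the interaction by 4 months gives, with the counts from step 3:

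| Late parents measured at months | Size of shift over 4 months |
|---|---|
| 1, 2 and 4 | 0.00-0.02 SD |
| 2 and 4 | 0.01-0.05 SD |
| 4 only | 0.02-0.09 SD |

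These values assume parallel courses. If late families change differently, the shift can be larger, and the documents give no figure from which to size it.

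**6. Precision if only entry parents are compared.** Retained per arm: 17.3 × 0.85 = 14.7. Scaling the plan's figure to 48% of families: .41/√0.48 = .59 SD (.82 at 25% entry, .47 at 75%). A plain two-sample calculation gives 2.802 × √(2/14.7) = 1.03 SD.

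**The case against.** **Baseline order.** A reader might infer that every parent gives a baseline after the youth's allocation. The documents do not say so. Involvement may begin at study entry, a supportive youth gives permission along with his own consent, and the Format paragraph has MySTYLE parents receiving content immediately after randomisation, as if already enrolled. The in-person consent step carried over from the formative phase concerns the son's participation, which the RCT waives for minors, so it is weak evidence of delay. The enrolment schematic is not in the available text and may show the order. What stands is that nothing in the text requires the parent baseline first.

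**Size.** A reader might also set 0.11-0.18 SD directly against .41 SD. The first is a shift in means and the second is for change; step 5 gives the like-for-like figure, which is small under parallel courses.

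**Waitlist data.** Nor does the problem take the same form however the waitlist conflict is settled. If the no-engagement sentence is literal, there are no waitlist parent reports at 2 or 4 months, hence no comparison to bias and also none to make.

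**Importance.** Late parent entry is a deliberate part of the intervention, the trial is a pilot, no parent-report model is written out, and the family scales have adolescent versions completed by all randomised youths. These points lower the severity. They do not make a comparison of all enrolled parents randomised.

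**Conclusion.** The concern holds for between-arm comparisons of parents' own reports that include everyone enrolled by 2 or 4 months. The mechanism follows from the text and needs no assumption. The sizes rest on the assumed 36 per arm, entry rate, conversion rate, gap and within-parent correlation: 0.11-0.18 SD in the arm mean, and about 0.00-0.05 SD (up to 0.09 SD) in the change contrast if courses are parallel. The mean shift runs against MySTYLE if late families score lower; once differential change is allowed, the direction for change scores is uncertain.

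Adolescent-report family scales and the behavioral outcomes are untouched. The no-engagement sentence and the parent payment schedule contradict each other and must be reconciled. This should be fixed, but it does not undermine the trial's main comparisons.

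**What to change.** 1. Record the youth's answer on parent contact before randomisation. Where he agrees at entry, obtain the parent's or caregiver's consent and online baseline before allocation, with a short cap on the wait (for example 14 days). After the cap, randomise the youth without a parent in the formal comparison.
2. Reconcile the Format paragraph with the Reimbursement section on whether waitlist parents are assessed at 2 and 4 months.
3. If they are, limit the between-arm parent-report analysis to parents with a pre-allocation baseline in both arms. If they are not, make no between-arm parent-report claim and rest the family-practice comparison on adolescent reports from all randomised youths.
4. Report parents who join later as engagement counts and descriptive scores only. They still receive the programme.

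The cost is wording and a delay of days for youths who agree at entry, plus the real loss of precision in step 6 of the working. Parent-report results should therefore be presented as estimates with intervals, not as tests.
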